5.3 Exclusion Criteria

1. History of high-risk pregnancy (e.g., placenta previa, history of preterm labor, preeclampsia).
2. Contraindications to exercise as defined by ACOG guidelines (e.g., ruptured membranes, incompetent cervix).
3. Taking sleep medication.
4. Severe musculoskeletal disorders preventing exercise.

6. INTERVENTIONS

6.1 Group A: Traditional Pregnancy Exercise (Intervention Group)

- **Description:** A structured exercise program specifically designed for pregnant women ("Senam Hamil").
- **Components:** Includes breathing exercises, muscle strengthening (pelvic floor,

abdominal), and relaxation techniques specifically standardized for pregnancy preparation.

- **Frequency:** [Insert Frequency, e.g., 1 session per week supervised + home practice].
- **Duration:** [Insert Time, e.g., 45 minutes per session].

6.2 Group B: Stretching Exercise (Active Control Group)

- **Description:** A regimen focusing on static stretching and flexibility.
- **Components:** Gentle stretching of major muscle groups (calves, hamstrings, lower back, neck) to relieve tension and improve circulation without the aerobic or intensive strengthening components of the traditional class.
- **Frequency:** Matched to Group A.
- **Duration:** Matched to Group A.

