4. STUDY DESIGN

4.1 Study Type

- **Type:** Interventional (Clinical Trial)
- **Design:** Quasi-Experimental (Non-randomized trial)
- **Allocation:** Non-randomized Parallel Assignment (Two Arms)
- **Masking:** Open Label (Participants and instructors know the intervention; Outcome assessors should ideally be blinded if possible).

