9.3 Safety Monitoring

Participants will be monitored for any adverse events (dizziness, contractions, pain). The intervention will be stopped immediately if any warning signs of pregnancy complications occur.

Figure S1. Traditional Pregnancy Exercise

No	Movement	Position	
1	Warm-up		
Position: Standing, feet shoulder-width apart.
 
Instructions:
 
 • Begin with slow breathing: inhale through the nose, exhale through the mouth. • Gently roll shoulders forward and backward 5–10 times. • Rotate the neck slowly in both directions. • March lightly in place for 1–2 minutes to warm the muscles. 
Purpose: Prepare the body, increase circulation, and reduce injury risk.

2	Deep Breathing and Chest Opening		
Position: Standing or sitting upright
 
Instructions:
 
 • Place both hands on the sides of the ribcage. • Inhale deeply, expanding the chest and ribs outward. • Exhale slowly while relaxing the shoulders. • Repeat 8–10 times. 
Purpose: Improve oxygenation, reduce tension, and promote relaxation.

[figure not shown]
[figure not shown]
3	Pelvic Tilts		
Position: Standing with back against a wall or on hands and knees
 
Instructions:
 
 • Gently tilt the pelvis forward and backward, tightening the abdominal muscles. • Avoid arching the lower back excessively. • Perform 10–12 repetitions. 
Purpose: Reduce lower-back discomfort and strengthen core stability.

4	Cat–Cow Stretch		
Position: Hands and knees (“tabletop” position)
 
Instructions:
 
 • Inhale while dropping the belly and lifting the head (cow). • Exhale while rounding the back and tucking the chin (cat). • Move slowly with the breath for 10 cycles. 
Purpose: Relieve back tension and improve spinal flexibility.

5	Hip Circles		
Position: Standing, hands on hips
 
Instructions:
 
 • Gently rotate the hips in a circular motion clockwise for 10 repetitions. • Repeat counterclockwise for another 10 repetitions.

[figure not shown]
[figure not shown]
			
Purpose: Loosen pelvic muscles and prepare for childbirth.

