6	Side Stretch		
Position: Standing or sitting
 
Instructions:
 
 • Raise the right arm overhead and gently bend to the left. • Hold for 10–15 seconds while breathing normally. • Switch sides and repeat. 
Purpose: Stretch the torso, reduce ribcage tightness, and improve breathing comfort.

7	Squat with Support		
Position: Standing, holding a chair or wall for balance
 
Instructions:
 
 • Slowly lower into a comfortable squat, keeping feet wide and knees aligned. • Hold for 5–10 seconds, then rise slowly. • Repeat 8–10 times. 
Purpose: Strengthen legs and pelvic floor, improve hip flexibility.

8	Butterfly Stretch		
Position: Sitting on the floor
 
Instructions:
 
 • Bring the soles of the feet together and let the knees fall outward. • Hold the ankles and gently press

[figure not shown]
[figure not shown]
			
the knees toward the floor.
 
 • Maintain the stretch for 20–30 seconds. 
Purpose: Open the hips and improve pelvic flexibility.

9	Pelvic Floor (Kegel) Exercise		
Position: Sitting or lying down
 
Instructions:
 
 • Contract the pelvic floor muscles as if stopping urine flow. • Hold for 5 seconds, then relax for 5 seconds. • Repeat 10–15 times. 
Purpose: Strengthen pelvic muscles to support pregnancy and childbirth.

10	Ankle and Leg Stretch		
Position: Sitting with legs extended
 
Instructions:
 
 • Point and flex the feet 10 times. • Rotate ankles clockwise and counterclockwise 10 times each. • Gently stretch the calves by pulling toes toward the body. 
Purpose: Improve circulation and reduce leg cramps or swelling.

11	Cool-Down and Relaxation		
Position: Sitting or lying on the left side
 
Instructions:
 
 • Take slow, deep breaths for 1–2 minutes.

[figure not shown]
			
• Relax the shoulders, jaw, and hands.• Visualize calmness and release tension throughout the body. 
Purpose: Lower heart rate, promote relaxation, and complete the session safely.

--	--	--	--

Figure S2. Stretching Exercise

No	Movement	Position	
1	Iskium Tibialis		
Lying on the surface, the therapist elevates the lower limb in extension and ankle dorsiflexion (3 x 20 sec repeats, bilaterally and alternately).

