2	Gluteus Maksimal		
Lying on the surface, with one lower limb in flexion and external rotation of the hip and knee, and the ankle resting on the contralateral thigh, the therapist manually increases hip flexion towards the opposite shoulder (3 x 20-second repetitions, bilateral and alternating).

3	Piriformis		
Lying on the surface with one lower limb in flexion and external rotation of the hip and knee, and the ankle resting on the contralateral thigh, the therapist manually conducts hip adduction towards the opposite lower limb (3 x 20-second repetitions, bilaterally and alternating).

4	Paravertebral		
Sitting on the edge of a surface with abducted lower limbs and feet resting on the floor. Perform trunk flexion for freight and sideways while supported up on a Swiss grid ball (3 x 15 sec reps, bilaterally and alternating).

5	Kuadratus Lumborum		
The therapist manually stretches the lumbar square in lateral decubitus, performing two 20-second repetitions on each side.

6	Latissimus Dorsi		
In a supine position with the upper extremities in 180° flexion, the therapist manually lateralises the pregnant woman's upper trunk to contralateral elongation (2 x 20 second repetitions, bilaterally).

7	Skalane		
The therapist conducts cervical rotation and flexion in a supine position to lengthen the contralateral scalene (2 x 20 second repetitions, bilaterally).

8	Trapezius		
The therapist conducts lateral tilt and cervical flexion to the contralateral trapezius in a supine position, with two 20-second repetitions performed bilaterally.

Source: (Fontana Carvalho et al., 2020)

Fontana Carvalho, A. P., Dufresne, S. S., Rogerio de Oliveira, M., Couto Furlanetto, K., Dubois, M., Dallaire, M., Ngomo, S., & da Silva, R. A. (2020). Effects of lumbar stabilization and muscular stretching on pain, disabilities, postural control and muscle activation in pregnant woman with low back pain. *Eur J Phys Rehabil Med*, 56(3), 297-306.
<https://doi.org/https://doi.org/10.23736/S1973-9087.20.06086-4>

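### Does the therapist wording in Figure S2 change what the trial compares?

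*Combined protocol and SAP*

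**What the plan says.** Section 6.2 defines Group B as "A regimen focusing on static stretching and flexibility". It lists the muscle groups, says the arm lacks the aerobic and intensive strengthening parts of Group A, and matches frequency and duration to Group A. It names nobody as applying the stretch.

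Figure S2, at the end of the document, is the only movement-by-movement description of Group B. Movement 1 reads "the therapist elevates the lower limb in extension and ankle dorsiflexion", movement 2 "the therapist manually increases hip flexion towards the opposite shoulder" and movement 5 "The therapist manually stretches the lumbar square in lateral decubitus, performing two 20-second repetitions on each side". Movements 3, 6, 7 and 8 also have the therapist acting. Only movement 4 is addressed to the woman: "Perform trunk flexion for freight and sideways while supported up on a Swiss grid ball". The figure is credited to a published study titled "Effects of lumbar stabilization and muscular stretching on pain, disabilities, postural control and muscle activation in pregnant woman with low back pain".

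Figure S1, for Group A, uses instructions to the woman throughout, for example "Gently tilt the pelvis forward and backward, tightening the abdominal muscles".

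Elsewhere, Section 2.3 speaks of women performing the exercises, Section 4.1 says "Participants and instructors know the intervention", and Section 6.3 relies on a participant logbook and an attendance record kept by the instructor.

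**The concern.** Read literally, Figure S2 makes Group B largely passive, hands-on treatment, while Group A is active exercise. Personal contact and passive movement would then differ between the arms along with exercise content. Because delivery mode would coincide with arm, the linear mixed model in Section 8.2 could not separate the two, whatever covariates it held.

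The stake is interpretation. Section 2.2 wants to tell providers which activity to prescribe. A result for stretching applied by a therapist does not show what stretching done by the woman herself achieves, and the reverse also holds. A reader might also credit a PSQI or HARS difference to exercise type when part of it came from individual attention.

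**Working it through.** **Count of who acts**

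| Source | Movements | Therapist named | Not named |
|---|---|---|---|
| Figure S2 (Group B) | 8 | 7 (nos. 1, 2, 3, 5, 6, 7, 8) | 1 (no. 4) |
| Figure S1 (Group A) | 11 | 0 | 11 |

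That Group A is self-performed is inferred from the imperative wording.

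**Does the main text contradict Figure S2?**

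- Section 6.2 names no agent. A stretch held by a second person can still be a static stretch.
- Section 6.3: the logbook records sessions, not who moves the limb. Supervised sessions are compatible with hands-on delivery.
- Section 4.1 mentions instructors only in the note on masking. Nothing rules out that the instructor is the therapist.
- Section 6.1 mentions home practice, which would sit badly with therapist-applied stretches, but only as an example inside an unfilled placeholder.
- Section 2.3 speaks of performing the exercises. This leans the other way, but it is the ordinary phrase for taking part in an exercise programme.

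One generic verb leans against the figure; the rest is silence.

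**Are the arms single-ingredient otherwise?** No. Section 6.1 gives Group A breathing, strengthening and relaxation together. Four of the 11 Figure S1 movements are themselves stretches by name (nos. 4, 6, 8 and 10). Section 3.1 compares two named regimens and does not claim to isolate one ingredient. So the trial compares packages whichever way the delivery question is answered.

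**How large is the therapist component?** The documents give no such figure, so I summed hold times from Figure S2 as repetitions × seconds × sides.

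- Full set on each side: movements 1–3 give 3 × (3 × 20 × 2) = 360 s and movements 5–8 give 4 × (2 × 20 × 2) = 320 s, so 680 s by the therapist. Movement 4, read as 45, 90 or 135 s, brings the total to 725, 770 or 815 s. Shares: 680/725 = 93.8%, 680/770 = 88.3%, 680/815 = 83.4%.
- Set shared between sides (movement 5 stays per side): 3 × 60 + 80 + 3 × 40 = 380 s by the therapist. Movement 4, read as 45 or 90 s, brings the total to 425 or 470 s. Shares: 380/425 = 89.4%, 380/470 = 80.9%.

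The range of 81–94% looks decisive, but its denominator is one pass of nominal holds: 425/60 = 7.1 to 815/60 = 13.6 minutes. Section 4.2 gives sessions of 45–60 minutes, that is 2,700–3,600 s. Against that, the therapist holds are 380/3,600 = 10.6% to 680/2,700 = 25.2% if the routine is done once, leaving out set-up and rest. The documents do not say how often it is repeated, so the actual contact share is unknown. The percentages add nothing reliable to the plain count of 7 in 8.

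**What would change under either answer?** If the stretches are therapist-applied, Group B is described that way in the report. If they are not, the Figure S2 text is a carry-over to be corrected. In both cases the assessments, the Section 8.2 model and the 60 participants are the same.

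**The case for a change.** The strongest case for a change is that Figure S2 is the only operational description of Group B, so anyone delivering or repeating the arm would follow it, and the main text does not prepare them for hands-on work. If the wording was carried over from the low-back-pain study, the figure misdescribes the arm; if it was not, Section 6.2 leaves out a notable feature. Either way a sentence is missing. The other differences between the arms are declared as exercise content in Sections 6.1 and 6.2, whereas hands-on delivery is not.

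Much of this stands. The description is incomplete, and the main text and Figure S2 should agree on who applies the stretches; which version is right is for the investigators. What does not follow is a revision of the design, hypothesis or objective. Recasting Sections 2.3 and 3.1 as an instructor-led programme against therapist-delivered stretching would assume a delivery mode for Group A that Section 6.1 does not give. It would also assume that instructor and therapist are different people, which the document nowhere states.

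**Conclusion.** No change to the plan follows. The facts are as described: 7 of 8 against 0 of 11, with no therapist in Sections 2.3, 4.1, 6.2 or 6.3. They amount to missing descriptive detail of a kind that the investigators fill when they write up the interventions. Delivery mode, if it differs, belongs to the treatment being compared. It is not a confounder of the comparison, and no adjustment or extra data would remove it.

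If the stretches were therapist-applied, a careful report would say that the result concerns stretching delivered that way and that hands-on contact differed between the arms. That bounds the conclusion without altering how the trial is run or analysed.

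The judgement rests on reading the main text as silent on delivery, and on text without the pictures, which might settle who acts. Any effect of hands-on contact on PSQI or HARS cannot be sized from the documents. Possible bias from non-random allocation is a separate matter that this point does not touch.

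### Figure S2 makes Group B mostly therapist-applied, which section 6.2 does not say, so the trial can compare the two regimens as delivered but not exercise type alone

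*Combined protocol and SAP*

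**What the plan says.** Section 6.2 introduces the comparator as "A regimen focusing on static stretching and flexibility". It lists the muscle groups, says that Group B leaves out the aerobic and more intensive strengthening work of the Group A class, and gives both frequency and duration as "Matched to Group A". It does not say whether the woman stretches herself or is stretched by someone else.

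Figure S2, at the end of the same document, gives the Group B content item by item. Item 1 reads "the therapist elevates the lower limb in extension and ankle dorsiflexion", item 2 "the therapist manually increases hip flexion towards the opposite shoulder", and item 5 "The therapist manually stretches the lumbar square in lateral decubitus". Figure S1 does the same for Group A, as instructions addressed to the woman.

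The primary objective (3.1) compares the two kinds of exercise on sleep quality. The rationale (2.2) wants the answer to guide which activity providers prescribe. The only staff member named in the body of the plan is an instructor who records attendance (6.3).

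**The concern.** Someone who reads only sections 2 to 8 would picture two programmes that women carry out themselves, differing in content and matched in how often and how long. Figure S2 describes something else for Group B: mostly passive stretching applied by a therapist. The declared contrast is exercise content. Hands-on treatment is a second systematic difference that the body of the plan does not mention.

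What is at stake is the conclusion. Advising a woman to stretch is a different recommendation from referring her to a therapist who stretches her. If the PSQI differs between arms, or does not, the plan as worded would credit exercise type, although the contrast also contains hands-on treatment. The trial is open label (4.1), so participants know which kind of treatment they receive.

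**Working it through.** The plan gives no count of its own to reproduce, so the check sets 6.2 beside the two figures.

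**Step 1. Who acts in Figure S2 (8 items).**

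- Item 1: "the therapist elevates the lower limb in extension and ankle dorsiflexion". Therapist.
- Item 2: "the therapist manually increases hip flexion towards the opposite shoulder". Therapist.
- Item 3: "the therapist manually conducts hip adduction towards the opposite lower limb". Therapist.
- Item 4: the woman bends her trunk over a Swiss ball. No therapist named.
- Item 5: "The therapist manually stretches the lumbar square in lateral decubitus". Therapist.
- Item 6: "the therapist manually lateralises" the woman's upper trunk. Therapist.
- Item 7: "The therapist conducts cervical rotation and flexion in a supine position". Therapist.
- Item 8: the therapist tilts and flexes the neck to lengthen the trapezius. Therapist.

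Result: 7 of 8 items are therapist-applied.

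**Step 2. Who acts in Figure S1 (11 items).** From warm-up to cool-down, every item instructs the woman. The only supports named are objects such as a wall or chair. Result: 0 of 11 items mention a therapist. The pictures are not available, so this count covers the text only.

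**Step 3. Does the item count exaggerate?** Prescribed hold time in one pass of Figure S2, counting both sides:

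- Items 1 to 3: 3 × 20 s × 2 = 120 s each, 360 s in all.
- Item 4: 3 × 15 s × 2 = 90 s.
- Items 5 to 8: 2 × 20 s × 2 = 80 s each, 320 s in all.

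Total: 360 + 90 + 320 = 770 s. Therapist-applied: 360 + 320 = 680 s. Share: 680/770 = 88%. If item 4 is held in a third direction (135 s), the share is 680/815 = 83%. Hold time agrees with the item count. The ratio does not depend on how many complete passes a session contains.

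**Step 4. Can the analysis separate contact from content?** Section 8.2 plans a linear mixed model for the group difference, adjusted for baseline score and confounders; 7.3 lists age, parity, BMI and gestational age. In its simplest form, with one row per woman, the model has 7 columns: intercept, arm, baseline score and four covariates. As prescribed, an indicator for hands-on treatment is 1 for every woman in Group B and 0 for every woman in Group A, so it repeats the arm indicator. A numerical check with 30 women per arm gave rank 7 for 7 columns, and still rank 7 for 8 columns once the contact indicator was added. In the repeated-measures form with arm by time, the rank was 9 for 9 columns and still 9 for 10. The contact effect cannot be estimated apart from arm. Neither randomisation nor a larger sample would change that.

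**Step 5. Compare with the objective.** The model estimates exercise content plus hands-on treatment as one quantity. Sections 2.2 and 3.1 word the question as being about type of exercise. The estimate answers the wider question of regimen against regimen.

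**The case against.** The strongest reply is that this is an ordinary comparison of two programmes. Each is spelled out in its own figure, and a short description backed by a detailed appendix is normal. Section 6.2 is silent on delivery; it does not contradict Figure S2, because static stretching can be done alone or by a therapist. That stands. A reader might infer that the protocol conflicts with its own appendix, and the text does not support this.

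Second, any component found in only one arm is inseparable from arm. The breathing, strengthening and relaxation work of Group A would fail the check in step 4 in the same way. That also stands. The covariate list in 7.3 is not deficient for omitting contact, since no covariate could do this job. What sets hands-on treatment apart is that it is not exercise content, and the body of the plan does not disclose it as part of the contrast.

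Third, a reader might infer that Group A receives no hands-on contact at all, or less staff contact overall. The documents do not show this. The pictures are missing, an instructor attends supervised sessions, and Group A's class size and instructor contact are not given. The supportable statement is narrower: prescribed in the text for Group B, not mentioned for Group A.

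Fourth, a reader might infer a biased result or an inflated false-positive rate. The documents give no size or direction for a contact effect. Contact could create a difference or hide one, and for the regimens as delivered any such difference is real.

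Finally, a reader might infer that matching would fail in home sessions. The frequency field in 6.1 is unfilled and its entry is only an example, so nothing can be built on it.

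The reply leaves one thing unanswered: 2.2 and 3.1 speak of exercise types, and the comparator's name does not tell the reader that it is mostly applied by a therapist.

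**Conclusion.** The point holds as a matter of labelling and interpretation. A therapist applies 7 of 8 items in Figure S2, and none of the 11 items in Figure S1 mentions one. Hands-on treatment and exercise content therefore differ together between the arms, and no analysis of this design can part them. A conclusion about which exercise type is better to prescribe is not supported; a comparison of the two regimens as delivered is the question this contrast can address. Non-random allocation is a separate matter and is not judged here.

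This rests on the two figures being delivered as written and on their text alone. The effect of contact on the PSQI cannot be sized from the documents, and no bias in a particular direction is claimed. It is a cheap improvement that changes what the trial may conclude, not a flaw that invalidates the comparison.

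**What to change.** State in 6.2 that the Group B stretches are applied by a therapist as set out in Figure S2. Name the comparator 'therapist-applied stretching' in 2.2 and 3.1. Add that conclusions refer to the two regimens as delivered, not to exercise type alone. These are text edits with no extra visits, staff or data, and they remain useful whether or not enrolment has begun. The price is that the trial gives up the claim that one type of exercise is better in itself.

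Optional, only before enrolment and only if the sponsor wants a contrast closer to exercise type: replace Figure S2 with stretches of the same muscle groups that the woman performs herself. This would remove the hands-on difference but not the other differences between the arms, such as breathing and relaxation work. Group B would also no longer follow the source cited for Figure S2.

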6.3 Adherence Monitoring

Participants will utilize a logbook to record exercise sessions. Attendance at supervised sessions will be recorded by the instructor.

